9.2.2. Exclusion Criteria

Patients meeting any of the following criteria will not be included in the study:

1. Patient has been exposed to any other ‘non-GO’ treatment regimen prior to treatment with GO for their AML (except leukoreduction with and without hydroxyurea).
2. Patient has been treated with GO only as a consolidation therapy and not as induction.

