4. ABSTRACT

Title: *GO-First*: Real-world treatment patterns and effectiveness outcomes associated with gemtuzumab ozogamicin (GO) in first-line AML.

Date: 19 October 2023, version 2.0; B1761038; [name], Pfizer R&D UK Ltd.

Rationale and background: AML is a complex and rare cancer of the bone marrow caused by genetic alterations in stem cells. In 2013, it was estimated that the incidence of AML in Europe was 5.06 patients per 100,000 people. The survival outcomes of AML patients are poor and treatment choice is influenced by various clinical characteristics including: type of AML, white blood cell count, cytogenetic risk groups and molecular mutations. Gemtuzumab ozogamicin (GO) [Mylotarg®] is an antibody-drug conjugate used for the treatment of AML patients with myeloid cells that express the CD33 receptor. The ALFA-0701 multi-centre Phase 3 trial demonstrated an estimated median event-free survival (EFS) of 17.3 and 9.5 months for patients receiving GO and chemotherapy or chemotherapy alone respectively, and 27.5 and 21.8 months for overall survival (OS). The results from this trial ultimately led to the approval of GO in the US and European Union.¹ There is limited knowledge of its real-world use and outcomes of GO in 1L treatment with the recent licensed dosing. This study will investigate the treatment patterns and effectiveness outcomes of 1L GO use on de novo AML patients in real-world healthcare, specifically those in the favourable and intermediate risk groups. This will allow the assessment of whether GO prescription patterns are aligned with licensed dosing/guidelines.

Research question and objectives:

This study aims to answer the following research question:

How is GO being used in real world clinical practice of de novo intermediate/favourable risk AML patients and what are the outcomes?

Co-Primary objectives

- To describe the patient demographics and clinical characteristics of patients treated with GO in intermediate and favourable cytogenetic risk, de novo AML.
- To describe GO treatment patterns in the study population, including the number of doses of GO and the timing of GO doses in 1L treatment.

Secondary objective

- To describe 1L treatment effectiveness outcomes for the study population, including:
 - Time-to-next treatment
 - Survival (event-free survival [EFS], relapse-free survival [RFS], overall survival [OS])

Exploratory objective:

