Each data source is likely to capture a large proportion of GO-treated patients in that country, hence their selection. The Austrian, Belgian and German centres have been selected as they meet the feasibility requirements (capture the relevant data variables) and due to the sample size of GO patients that they contain. The Austrian Myeloid Registry recruits data on patients with myeloid diseases from 15 Austrian centres (excluding the Medical University of Vienna) with an estimated enrollment of 3000 patients. The eligibility criteria below are largely based upon the recommend use of GO; ensuring that the overall patient sample gathered will be clinically representative of the GO treated population.

The initiation date of 1L treatment within the indexing period will be defined as the index date. De novo AML diagnosis will be captured within the screening questions of the eCRF and fully defined for each data source within the Statistical Analysis Plan (SAP). Baseline patient demographics and clinical characteristics will be evaluated at index. Treatment patterns and effectiveness outcomes will be described throughout the follow-up period. Patients will have a minimum follow-up of 3 months defined as patients with 3 months of data, following the 1L treatment initiation. This will allow for assessment of treatment patterns and early effectiveness outcomes. Follow-up will end with the following endpoints: death, loss of data (eg, transfer to a new hospital) or end of the study period. In order to maximise the follow-up data captured necessary to accurately assess survival outcomes (EFS, RFS and OS), follow-up will extend up until either the last data available for the patient (in Austrian, Belgium, and German sites), or the date of database extraction (in the Austrian Myeloid Registry). Patients who have limited follow-up data which is not sufficient for the assessment of OS and accurate EFS and RFS, will be right-censored for the purpose of survival outcome specific analysis. Patients who die within the 3-month follow-up period would be considered eligible for inclusion in order to evaluate EFS, RFS and OS outcomes.

Figure 1. Study Schematic

Study Schematic–eCRF and secondary data dataset design

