9.2.1. Inclusion Criteria

Patients must meet all of the following inclusion criteria to be eligible for inclusion in the study:

1. Patient has a clinical diagnosis of **de novo** AML.
2. Patient is aged 18 years or older.
3. Patient has a cytogenetic risk stratification of 'favourable' or 'intermediate (classified according to the International System for Human Cytogenic Nomenclature criteria.¹³

4. Patient has been treated with GO in a 1L induction setting in a combination chemotherapy treatment.
5. Patient has data points available for a minimum of 3 months data from the first GO-containing regimen (index). Patients who die within the 3 months are eligible for inclusion within the study.
6. *For patients from Austrian, Belgium, and German sites:* Evidence of a personally signed and dated informed consent document indicating that the patient (or a legally acceptable representative) has been informed of all pertinent aspects of the study.
Note – may not be required and depends on individual country/site IRB guidance.

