9.3.2. Outcomes

9.3.2.1. Treatment Patterns

The treatment landscape for GO will be described for all de novo AML patients treated with the drug as a 1L therapy. The following will be assessed to describe the overall treatment pathway for each patient:

Pharmacological treatment

- **Lines of therapy (LoT):** The number of LoT received by a patient from and including the index date, to the end of their observation period will be reported as a categorical (1, 2) numeric variable
- **Treatment regimen:** The number and percentage of patients receiving a given treatment regimen will be reported for each LoT, up to 2 LoT – defined as the combination of drugs (including GO)
- **Treatment setting pathway:** The treatment setting by regimen will be reported as a categorical variable using the following groups:
 - Induction, consolidation

The number of patients receiving GO in induction **AND** consolidation (in succession) will also be reported.

- **Number of doses per regimen:** The number of doses of GO in the first-line treatment regimen, broken out by first-line induction and first-line consolidation. This will be reported as a categorical (1, 2, 3, 4+) numeric variable.
- **Dosing per administration:** Actual total dose (mg) administered for GO will be reported for the first-line treatment regimen, broken out by first-line induction and first-line consolidation. This will be reported as a categorical (1, 2, 3, 4+) numeric variable.
- **Time between dosing:** Time in days between the combined chemotherapy and GO initiation (and vice versa) and time in days between each GO dose will be reported as continuous numerical variables. *Subject to availability – as multiple doses of GO are captured as one regimen; this information may not be explicitly available.*
- **Cytogenetic complete response:** Recorded for each LoT as a categorical variable:
 - Yes, No, Not examined, Undisclosed

Stem cell transplants

- **Stem cell transplants:** The occurrence of a haematopoietic stem cell transplant (HPSCT) [allogeneic or autologous] will be reported as a binary categorical variable – ‘Y’ or ‘N.’ The type of transplant will not be reported.

The feasibility of capturing/defining these data points will be assessed upon communication with data custodians and sites. Details of variable definitions will be captured in the SAP.

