9.3.3. Covariates

9.3.3.1. Baseline Patient Characteristics

The following characteristics will be captured at baseline – the data point closest to the index date will be used:

- **Index date:** The month and year of the patient's index date (start of 1L treatment) will be identified and reported:
 - January, February, March, April, May, June, July, August, September, October, November, December
 - 2018, 2019, 2020, 2021, 2022
- **Age:** Age (in years) as of index date will be reported as a numeric value and categorised as follows:
 - ≥ 18 years and < 30 years, ≥ 30 years and < 40 years, ≥ 40 years and < 50 years, ≥ 50 years and < 60 years, ≥ 60 years and < 70 years, ≥ 70 years and < 80 years, or ≥ 80 years
- **Biological Sex:** *Male or female*; patients with sex stated as unknown will be classified as missing data for the purpose of this analysis.
- **Body Mass Index (BMI):** Weight in kilograms divided by height in meters squared, will be utilised as either a continuous variable or a categorical variable using the following categories: Underweight (Below 18.5), Normal (18.5 - 24.9), Overweight (25.0 - 29.9), Obese (30.0 – 34.9) and Morbidly obese (35.0 and greater). Most recent measurement prior to and including index date will be reported. If BMI is provided explicitly, patients will be categorised into these groups if and where appropriate.

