 - *2 – Ambulatory and capable of all selfcare but unable to carry out any work activities. Up and about more than 50% of waking hours;*
 - *3 – Capable of only limited selfcare, confined to bed or chair more than 50% of waking hours;*
 - *4 – Completely disabled. Cannot carry on any selfcare. Totally confined to bed or chair;*
- **Level of leucocytes [m/L]:** Captured at the time closest to index will be reported as a continuous numerical variable.
- **Level of thrombocytes [m/L]:** Captured at the time closest to index will be reported as a continuous numerical variable.
- **Level of lactate dehydrogenase (LDH) [U/L]:** Captured at the time closest to index will be reported as a continuous numerical variable.
- **Bone marrow blasts [%]:** Captured at the time closest to index will be reported as a continuous numerical variable.
- **Peripheral blood marrow blasts [%]:** Captured at the time closest to index will be reported as a continuous numerical variable.

Categories for variables will be further defined upon receipt of data within the SAP.

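### Leukoreduction before GO is allowed but is not a listed variable, so leucocyte and peripheral-blast values taken nearest index mix lowered and untreated counts without a marker

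*Protocol*

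**What the plan says.** All references are to the Protocol.

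- **Eligibility.** Exclusion 1 in Section 9.2.2 rules out earlier non-GO regimens for AML, with one exception: "except leukoreduction with and without hydroxyurea".
- **Index.** Section 9.2: "The initiation date of 1L treatment within the indexing period will be defined as the index date". Inclusion criterion 5 in Section 9.2.1 ties index to the first regimen that contains GO.
- **Baseline anchor.** Section 9.2: "Baseline patient demographics and clinical characteristics will be evaluated at index".
- **Leucocytes and peripheral blasts.** Section 9.3.3.2, for each: "Captured at the time closest to index will be reported as a continuous numerical variable". For BMI, by contrast, Section 9.3.3.1 sets a limit in time: "Most recent measurement prior to and including index date will be reported".
- **Treatment variables.** Section 9.3.2.1 starts the count of treatment lines at index: "The number of LoT received by a patient from and including the index date, to the end of their observation period".
- **What is not listed.** In the text at hand, leukoreduction and hydroxyurea appear only in Section 9.2.2. Section 9.3.3.2 captures the date of diagnosis but ties no blood count to it. The limitations in Section 9.9 do not mention the matter.
- **Relevance by the protocol's own account.** The Abstract states that "treatment choice is influenced by various clinical characteristics including: type of AML, white blood cell count". Section 7 adds leucostasis to the same list.

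**The concern.** Describing the clinical characteristics of GO-treated patients is a co-primary objective. Section 9.7 reports means, SDs, quartiles and maxima for continuous variables, and Section 9.9 relies on comparing baseline data with published datasets to judge how far the results generalise.

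Leukoreduction acts directly on the leucocyte count. If it is given before index, the value nearest index describes the patient after that step, while the value of an untreated patient describes the disease as it presented. The two kinds of value go into one summary with nothing to tell them apart. If the treated patients are those who presented with the highest counts, which is plausible but not stated, the upper tail is the part that is lost. A comparison with a dataset that reports counts at presentation would then make this cohort look lower in disease burden than it was.

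**Working it through.** **1. The plan's own figure.** The only computable figure nearby is the expected sample size. Table 1 gives 50 + 30 + 50 + 42 + 18 + 40 = 230, as stated. The point does not affect it.

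**2. Order of events.** The exception covers leukoreduction before GO. Index is the start of first-line treatment or of the first GO-containing regimen. When these coincide, the exempted leukoreduction precedes index. They need not coincide: Section 9.3.2.1 plans to measure the time between chemotherapy and GO in either order. If chemotherapy starts first, leukoreduction before GO could fall after an index set at the start of first-line treatment. So the nearest-index value is normally, not always, the lowered one.

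**3. Direction of the open window.** The leucocyte rule does not require the value to be on or before index, as the BMI rule does. A value drawn just after chemotherapy starts is therefore admissible, and would tend to err in the same downward direction.

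**4. Can the affected values be found?** Not from the listed variables: the treatment variables begin at index, and the baseline list has no leukoreduction item and no count at diagnosis.

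**5. Size, on assumptions only.** The documents give neither the share leukoreduced nor the fall. For illustration, assume a lognormal presenting count with median 10 (arbitrary units) and log-SD 1.5. Let the highest share f of patients be cut to a fraction r of their presenting count.

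- Presenting mean = 10 × exp(1.5²/2) = 30.8; presenting Q3 = 27.5.
- Share of the total count held by the top f: Φ(1.5 − z), where z is the (1 − f) normal quantile.
- Relative fall in the mean = (1 − r) × Φ(1.5 − z).
- Example, f = 0.10, r = 0.5: z = 1.28, Φ(0.22) = 0.586, fall = 0.5 × 0.586 = 29%.

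| f (patients of 230) | r = 0.7 | r = 0.5 | r = 0.3 |
|---|---|---|---|
| 5% (12) | −13% | −22% | −31% |
| 10% (23) | −18% | −29% | −41% |
| 20% (46) | −22% | −37% | −52% |
| 30% (69) | −25% | −42% | −58% |

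The entries are changes in the mean. The median stays at 10.0 in every cell except the last (f = 30%, r = 0.3), where it is 8.3. Q3 stays at 27.5 when 5% are affected and falls to 14.5 (−47%) in the most extreme cell.

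**The case against.** The strongest reply is that the protocol chose index as its baseline, and a count taken nearest index is correct for that target. No objective names the count at diagnosis. This stands. A reader might infer that the leucocyte description is wrong, or that baseline should move to diagnosis; the documents support neither. The value is low only relative to presentation.

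Second, Section 9.3 leaves the final variables to the SAP, Section 9.4 says abstraction is not limited to the listed items, and the eligibility screener has to apply exclusion 1 with its exception. The eCRF, screener and SAP are not shown. A reader might infer that leukoreduced patients can never be identified; that goes too far. What is shown is only that no listed variable identifies them. The reply does not settle the matter, however. Section 9.3 says the CRF already covers every variable of interest, and a SAP cannot analyse what was not abstracted. In Germany (40 of 230 expected patients, 17%) Sections 9.6 and 9.8 allow no linkage, so a missed item cannot be recovered. Elsewhere the linkage is deleted at site close-out.

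Third, any percentage is produced by its assumptions, and Section 9.7 also reports medians and quartiles. This stands in full. A reader might also infer that high counts disappear from the results. That would require every leukoreduced patient to drop below a cut-off with no other patient above it, and leucocytes are listed only as a continuous variable.

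Fourth, the comparison in Section 9.9 does not single out leucocytes and names no comparator or time point, and the count enters no eligibility criterion or effectiveness definition. This stands and limits the consequence to the descriptive tables. LDH follows the same nearest-index rule, but nothing here makes the case for redefining it.

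**Conclusion.** The point holds as a cheap improvement to the data collected. Followed as written, the rules combine treatment-lowered and untreated leucocyte and peripheral-blast values in a co-primary description, with no listed variable to separate them. The mean, SD and maximum are affected, and Q3 may be if enough patients were leukoreduced; the median is largely robust.

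The documents do not allow the amount to be estimated. The 13% to 58% fall in the mean is a sensitivity range that rests on an assumed lognormal count, an assumed share of patients, an assumed reduction, and the assumption that the patients treated are those with the highest counts. The conclusion also assumes that leukoreduction usually precedes index and that the unseen eCRF matches the listed variables. Sample size, eligibility and the effectiveness endpoints are not affected.

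**What to change.** In Section 9.3.3.2 and the eCRF:

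1. Add an item for leukoreduction or hydroxyurea before index (yes/no, start date).
2. Keep the index value for leucocytes and peripheral blasts, but limit it to on or before index, as is done for BMI.
3. For flagged patients, also capture the last leucocyte and peripheral-blast value before leukoreduction.
4. Report both values. Use the pre-leukoreduction value when comparing with published datasets that report counts at presentation.
5. Request the same items from the Austrian Myeloid Registry where it holds them.

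The limit in step 2 does not replace the flag, because the last value before index may itself be the lowered one. The items need to be in the eCRF at first entry, given the anonymised German data.

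The cost is one extra item for all patients and one extra laboratory set for flagged patients. That set may be unavailable in the registry (about 30 patients), in which case the gap should be reported. No eligibility rule, sample size or aspect of patient care changes.

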9.3. Variables

This study will bring together different data sources that will be harmonised to have common variables and allow for analysis of one multi-country combined dataset. The variables below and the CRF were designed using knowledge of datasets known to collect data from medical records. All data variables present in the Austrian registry are not explicitly known but are likely to cover those listed below. The CRF captures all data variables of interest therefore allowing research objectives to be addressed. Final variables will be confirmed upon finalisation of the data sources within the SAP. Data sources have been selected following feasibility assessments, whereby the presence of the variables below will be assessed within the data captured.

9.3.1. Exposures

GO use

Patients have been treated with GO in a 1L chemotherapy regimen for AML. GO must be administered concomitantly with induction chemotherapy, ie, between the start and end date of a patient’s 1L therapy regimen they have received GO and another chemotherapy drug between the indexing period outlined in [Section 9.2](#).

9.3.2. Outcomes

9.3.2.1. Treatment Patterns

The treatment landscape for GO will be described for all de novo AML patients treated with the drug as a 1L therapy. The following will be assessed to describe the overall treatment pathway for each patient:

Pharmacological treatment

- **Lines of therapy (LoT):** The number of LoT received by a patient from and including the index date, to the end of their observation period will be reported as a categorical (1, 2) numeric variable
- **Treatment regimen:** The number and percentage of patients receiving a given treatment regimen will be reported for each LoT, up to 2 LoT – defined as the combination of drugs (including GO)
- **Treatment setting pathway:** The treatment setting by regimen will be reported as a categorical variable using the following groups:
 - Induction, consolidation

The number of patients receiving GO in induction **AND** consolidation (in succession) will also be reported.

- **Number of doses per regimen:** The number of doses of GO in the first-line treatment regimen, broken out by first-line induction and first-line consolidation. This will be reported as a categorical (1, 2, 3, 4+) numeric variable.
- **Dosing per administration:** Actual total dose (mg) administered for GO will be reported for the first-line treatment regimen, broken out by first-line induction and first-line consolidation. This will be reported as a categorical (1, 2, 3, 4+) numeric variable.
- **Time between dosing:** Time in days between the combined chemotherapy and GO initiation (and vice versa) and time in days between each GO dose will be reported as continuous numerical variables. *Subject to availability – as multiple doses of GO are captured as one regimen; this information may not be explicitly available.*
- **Cytogenetic complete response:** Recorded for each LoT as a categorical variable:
 - Yes, No, Not examined, Undisclosed

Stem cell transplants

- **Stem cell transplants:** The occurrence of a haematopoietic stem cell transplant (HPSCT) [allogeneic or autologous] will be reported as a binary categorical variable – ‘Y’ or ‘N.’ The type of transplant will not be reported.

The feasibility of capturing/defining these data points will be assessed upon communication with data custodians and sites. Details of variable definitions will be captured in the SAP.

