Gemtuzumab ozogamicin (GO) [Mylotarg®] is an antibody-drug conjugate used for the treatment of AML patients with myeloid cells that express the CD33 receptor.¹⁰ The FDA approved GO for the treatment of newly diagnosed CD-33-positive AML in September 2017.¹ for use alone or in combination with chemotherapy, depending on the characteristics of the patient. In April 2018, GO received marketing authorisation from the EMA for the European Union, to be used in combination with daunorubicin and cytarabine chemotherapy.^{11,12} The ALFA-0701 multicentre Phase 3 trial results demonstrated the effectiveness of GO, which ultimately led to its approval. Patients aged 50-70 years old with newly-diagnosed de novo AML were treated with GO in combination with daunorubicin and cytarabine chemotherapy. The trial demonstrated an estimated median event-free survival (EFS) of 17.3 and 9.5 months for patients receiving GO and chemotherapy or chemotherapy alone respectively and 27.5 and 21.8 months for overall survival (OS).¹

Over the years GO has been studied in multiple different combination regimens and different dosing schemes.¹² There is limited knowledge of its real-world use and outcomes as first line treatment with the recent licensed dosing (ie, 3 doses during the induction cycle). Using results from a feasibility study conducted by Adelphi Real World (ARW) and contacts with data source custodians, evidence suggests that 1L treatment with GO has been used to treat AML patients in several countries. Pfizer would like to conduct a study investigating the treatment patterns and effectiveness outcomes of 1L GO use on de novo AML patients in real-world healthcare, specifically those in the favourable and intermediate risk groups. This will allow the assessment of whether GO prescription patterns are aligned with licensed dosing/guidelines and will provide novel insights into whether the observed real-world outcomes associated with these prescription patterns are effective. The study will use a combination of AML specific data sources and a retrospective medical chart review using a Case Report Form (CRF) to conduct a multi-country study with Belgium and Austria. Such data sources were identified during a feasibility assessment and were deemed to likely capture a sufficient sample size of patients (according to the eligibility criteria outlined in [Section 9.2](#)).

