9.9. Limitations of the Research Methods

Study design limitations:

- The overall sample size of patients (~230) may limit comparisons if subgroup numbers are low, such as ELN risk status (intermediate and favourable) and cytogenetic risk subgroups. However, the sample size is not substantially low in relation to the global population of interest. Furthermore, this is purely a descriptive study with no statistical comparisons and so the assessment of treatment patterns and effectiveness outcomes will not be affected by the small sample sizes.
- As this a multi-county multisource study, it is likely that there will differences in data variable availability. To mitigate this, the eCRF used for Austrian, Belgian, and German sites will be designed using knowledge of datasets known to collect data from medical records. When requesting data from the Austrian Myeloid Registry, variables will be requested in this same format where possible. Furthermore, during analysis where specific variables or outcomes cannot be assessed/described in one data source, subgroup analyses could be conducted for a subset of patients from certain data sources.
- GO-based treatment regimens and dosing schedules may differ through the different countries, adding to the complexity of the assessment of effectiveness outcomes. Subgroup analyses could be conducted for subsets of patients receiving the same or similar treatment regimens and or dosage schedules. Furthermore, dosing information per regimen may not be available in the data sources. For example, a total dose of GO may be provided, without numbers and/or timings. Nevertheless, number of doses is likely to be imputable due to prescribing guidelines and consistent quantities of GO supplied in vials (each dose). Timings of doses could be derived algorithmically, details of which would be provided in the SAP.
- The multiple cytogenetic risk groups included in the study cohorts, could similarly add complexity to the assessment of effectiveness outcomes. As a result, the analyses could include a stratification of risk group, subject to sample sizes.

- The minimum follow-up period has been set to 3 months. Consequently, for a large number of patients, OS and EFS maybe not assessable. These patients will be censored for such analyses.

Data source related limitations:

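### The listed GO dosing variables cannot separate a shorter intended schedule from one cut short, so the promised comparison of prescribing with licensed dosing is not supported as written

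*Protocol*

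**What the plan says.** Section 7 of the protocol states a purpose: "This will allow the assessment of whether GO prescription patterns are aligned with licensed dosing/guidelines". The Abstract (Section 4) repeats it. Section 7 also names the benchmark, "recent licensed dosing (ie, 3 doses during the induction cycle", so the comparison is chiefly one of dose counts.

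Section 9.3.2.1 lists the GO dosing variables:
- The count: "The number of doses of GO in the first-line treatment regimen, broken out by first-line induction and first-line consolidation". On its form: "This will be reported as a categorical (1, 2, 3, 4+) numeric variable".
- The amount: "Actual total dose (mg) administered for GO will be reported for the first-line treatment regimen".
- The interval between GO doses, subject to availability.

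The count item does not itself use the word administered. In a retrospective chart review, and beside an amount item that does, doses received is the natural reading. Section 9.3.2.1 lists no planned schedule, no item for stopping GO and no reason for fewer doses.

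Section 9.2.1 keeps early deaths: "Patients who die within the 3 months are eligible for inclusion within the study". Section 9.2 gives the reason: "Patients who die within the 3-month follow-up period would be considered eligible for inclusion in order to evaluate EFS, RFS and OS outcomes". Neither section says how these patients enter the dosing summaries.

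Where a source gives only a total dose, Section 9.9 says the "number of doses is likely to be imputable due to prescribing guidelines and consistent quantities of GO supplied in vials (each dose".

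**The concern.** Prescribing is a decision. The dose count is the result of that decision plus what happened to the patient afterwards. A patient meant to receive three induction doses who died or had GO stopped after one falls in the same category as a patient for whom one dose was planned. With the benchmark stated as a dose count, a reader of the final table will tend to take one or two doses as a departure from the licence, and the listed variables give no means of checking that.

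Imputed counts raise the opposite problem. A number filled in from guidelines is partly determined by the standard against which it would then be compared.

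Section 9.1 also aims to assess differences in treatment patterns between countries. If early death or early stopping differs between countries or sources, or if imputation is used in some and not in others, those differences could look like differences in prescribing.

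**Working it through.** **Stated figure.** Section 9.5, Table 1: 50 + 30 + 50 + 42 + 18 + 40 = 230, which agrees with the approximate total in Sections 4 and 9.4. The study is descriptive, so no power calculation applies.

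**Assumed inputs.** The protocol gives neither of these, so the results are illustrations and not estimates.
- p, share of patients intended to receive three induction doses: 50% to 100%.
- q, share of those who die or stop before the third dose: 2% to 15%.

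**Step 1: truncation alone.** Observed three-dose share = p × (1 − q). Shortfall = p × q. Patients affected = 230 × p × q. The 95% half-width is 1.96 × √[s(1 − s)/230], where s is the observed share.

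With p = 90%:

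| q | Observed share | Shortfall (points) | Patients of 230 | 95% half-width (points) |
|---|---|---|---|---|
| 2% | 88.2% | 1.8 | 4 | 4.2 |
| 5% | 85.5% | 4.5 | 10 | 4.6 |
| 10% | 81.0% | 9.0 | 21 | 5.1 |
| 15% | 76.5% | 13.5 | 31 | 5.5 |

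Over the full ranges, the smallest shortfall is 0.50 × 0.02 = 1.0 point (about 2 patients) and the largest is 1.00 × 0.15 = 15.0 points (about 35 patients). Half-widths run from 1.8 to 6.5 points. Truncation can therefore be negligible or exceed sampling error.

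**Step 2: adding imputation.** Suppose a share m of patients have imputed counts and, as an extreme, all are set to three. Observed share = (1 − m) × p × (1 − q) + m. For illustration, take m as the registry's share in Table 1, 30/230 = 13.0%. The protocol does not say which source would need imputation.
- p = 90%, q = 10%: 0.870 × 0.810 + 0.130 = 83.5%, which is 6.5 points below the true 90%.
- p = 50%, q = 5%: 0.870 × 0.475 + 0.130 = 54.3%, which is 4.3 points above the true 50%.

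The sign of the error changes within the assumed ranges, so its direction cannot be stated.

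**Step 3: could the analysis stage repair this?** Overall survival runs from the start of first-line treatment to death (Section 9.3.2.2). With dose dates, some early deaths could be identified as truncations, but Section 9.3.2.1 warns that dose timing may not be available. Stopping in surviving patients is harder: Section 9.3.2 lists no toxicity item apart from two events after stem cell transplant. A reason that was never abstracted cannot be derived later. The German data (40 of 230, or 17%) are fully anonymised, so sites cannot re-identify a patient to answer a query (Sections 9.6, 9.8 and 9.9). Elsewhere the linkage is destroyed at site close-out (Sections 9.6 and 10.1).

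**The case against.** A reader might infer that patients who died or stopped early will be counted as having been prescribed a non-licensed schedule, and that the report will understate agreement with the licence. The protocol does not support that. It reports a distribution of dose counts and defines no aligned or not-aligned class, no denominator and no rule for early deaths. Nor is a one-way bias established, since the imputation in Section 9.9 acts in the opposite direction.

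It can also fairly be said that:
- The co-primary objective in Section 8 is to describe treatment patterns, and doses received measure that correctly. The alignment sentence stands in the rationale and is not a listed objective.
- Only deaths within the induction dosing span can shorten the induction count, so the three-month rule overstates the exposure, and some of those deaths can be identified.
- The eCRF and the SAP are not shown. Section 9.3 says the CRF covers all variables of interest, and Section 9.4 leaves the list of abstracted data open.
- Sites may enter only what is in the medical record (Section 9.4). Planned doses may be sparsely recorded, and judging alignment only where a plan is found would give a selected denominator.

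These points stand and limit the finding. The co-primary description is not mis-measured, and the absence is from the variables listed in the protocol. They do not rescue the alignment statement. An open list permits further items but commits to none, and a SAP cannot supply reasons that were not abstracted.

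**Conclusion.** The point holds in a limited form. The dosing variables in Section 9.3.2.1, with the imputation allowed in Section 9.9, cannot separate a shorter intended schedule from one cut short by death or early stopping. The statement in Sections 4 and 7 that the study will assess whether prescribing is aligned with licensed dosing is therefore not supported as written.

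The size and direction of any error are unknown. The range of 1 to 15 percentage points for truncation rests wholly on assumed rates, and guideline-based imputation could offset or reverse it. What is affected is the conclusion about prescribing, not the description of doses received. The matter should be settled before abstraction, because missing reasons may not be recoverable later. No position is taken on which dosing schedule is right.

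**What to change.** 1. Add to the eCRF the reason when GO was stopped or fewer doses were given than intended: death, toxicity, change of plan, other, or not recorded. Add the planned number of doses where the chart records it.
2. Report the dose-count distribution for all patients, with those who died or stopped GO before completing the planned course shown separately.
3. Do not use guideline-imputed counts as evidence of alignment.
4. Where intent or reason is not recorded, for example in the registry, describe doses received only and make no statement about prescribing. Word the sentence in Sections 4 and 7 to match.

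The cost is slightly longer abstraction, some answers of not recorded, and inclusion in an amendment, which needs prospective ethics approval (Section 10.4). The Abstract puts the start of data collection at 1 November 2023, after the protocol date of 19 October 2023, so on that date the items could precede first entry. Section 6 prints a 2024 start that falls after its own end date, so the actual start should be confirmed. If abstraction has begun, the German records already entered probably cannot be completed, and item 4 applies to them.
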